Current status	
Since the first wave of COVID-19, pulmonologists, cardiologists and physiologists are regularly consulted for intolerance to exercise expressed by dyspnea and/or frank fatigability sometimes associated with muscular or thoracic pain. When these complaints persist beyond 3 months after the first symptoms, it is legitimate to perform a CPET:
 
 
• Either to evaluate the functional impact of an identified organ deficiency (e.g. myocarditis, pulmonary fibrosis, etc.),
 
• Or, in the absence of formal arguments for an identified organ deficiency, to observe possible abnormalities in physiological responses during an incremental exercise test, likely to explain the persistence of symptoms and intolerance to exercise.
 
 
The recent literature highlights the presence of non-specific ventilatory and cardio-circulatory abnormalities leading to various physio-pathological observations. These reports concern today relatively small numbers of patients mixing subjects whose clinical forms of COVID, comorbidities and habitus are very diverse. Moreover, the hypotheses or conclusions proposed by these studies are influenced by the medical specialty of the practitioner who observes them.
 
Thus, it seems necessary to collect a very large number of clinical and physiological observations in order to draw up a factual report of the disorders observed without any interpretative preconception.
 
It is reasonable to assume that, with time, health professionals will be frequently confronted with patients with exercise intolerance after COVID-19 and that the management of the disease will be more codified. For this, it seems necessary to collect and secure as much data as possible in order to improve the understanding of persistent symptoms and in particular the potential diversity of phenotypic presentations.

Objectives	Primary objective:

	
Physiological responses and symptoms during CPET in subjects diagnosed with COVID who have persistent symptoms responsible for exercise intolerance
 
Homogeneous patient subgroups will consider:
 
 
the initial clinical presentation of COVID,
 
any persistent symptoms other than exercise intolerance,
 
clinical characteristics prior to COVID-19 infection (co-morbidities – regular habitual physical activity).
 
 
Secondary objectives:
 
 
To model the kinetics of ventilatory pattern responses in order to characterize the behavior of excessive hyperventilation and, possibly, chaotic breathing.
 
To test, through different statistical models, the possibility of predicting the persistence of dyspnoea as a function of exercise variables, pre-existing clinical data of the COVID, clinical presentation of the acute COVID.
 

Concerned population	
Inclusion criteria:
 
 
Age <math>\geq</math> 18 years
 
Patients with persistent symptoms 3 months after the onset of COVID-19 infection, regardless the severity of the initial illness
 
Patients with an ICU stay, primarily following rehabilitation management; that is, in practice, at least 6 months after COVID
 
Patients followed by a pulmonologist, cardiologist or physiologist in a public or private facility or in private practice, allowing for CPET
 
Patients who have performed a CPET before December 31, 2022
 
Patients informed of the possible anonymized processing of the data collected during CPET for research purposes; and who gave informed consent
 
 
Exclusion criteria:
 
 
Age <math><</math> 18 years
 
Patients unable to perform CPET for locomotor reasons
 
Patients with severely reduced functional work capacity
 
Patient deprived of liberty by judicial or administrative decision
 
Patients unable to give informed consent
 

Study type and methodology	
French-speaking, multicentric, observational, descriptive cohort study with retrospective data collection, not affecting the management of patients and in line with the French MR004 reference methodology.
 
The following processes are defined in this protocol:
 
 
on-site collection of clinical and physiological data from patients process;
 
anonymization and migration process of these data (collected on each investigation site) to the centralized CPET-studies.com platform which will return an anonymized file dedicated to statistical analysis.
 

Recruitment	
Investigator Recruitment
 
From June 1, 2022, pulmonologists, cardiologists and physiologists performing CPET in public or private structures (Univ. Hospital, General Hospital, private practice or mixed activity) will be invited to participate in this study.
 
Patient Recruitment
 
From February 1, 2023, each investigator will be able to identify the files of patients who meet the inclusion criteria of the protocol by going back to January 2, 2020.
 
From February, 2023, each investigator will be able to ensure the migration on the CPET-studies.com platform of clinical and physiological data collected between January 2, 2020 and December, 2023.

Data collection	
Physiological data collection
 
Physiological measurements made during CPET (source data) will be stored locally on each investigator's ergospirometer until the time of migration.

	
They include continuous recording of ergospirometer measurements and discontinuous recording of blood pressure, symptoms and blood gases.
 
In order to get rid of some of the variability of the results the export will only concern the measured data. Additional physiological data will then be obtained by applying the appropriate physiological calculation formulas in a strictly identical way whatever the brand of the ergospirometer. All these data (measured and calculated) will be transformed by the CPET-STUDIES application into a file called Finalized File.
 
Collection of clinical data
 
The clinical data of the patients will be collected on the medical file or a dedicated file (Excel or Word) by each practitioner. They will be filled in by the referring physician who alone knows the name and surname of his patients on the online platform. The identifying data of each patient will then be pseudonymized so that no one other than the referring physician can access them. All data is hosted by a health data host certified for the 6 HDS levels.
 
Clinical data are: sex, weight, age, height, date of COVID, physical activities before COVID, comorbidities, COVID-related symptomatology, usual treatments, Hospital Anxiety and Depression Scale (HADS) and Chalder fatigue scale questionnaires.
 
Access to the platform will be secured by identification with a login and a password
 
The patient's physiological and clinical data will be encrypted and pseudonymized when migrated and/or entered on the CPET-STUDIES.COM platform.
 
The content of the Finalized File will then be imported into a database, which contains only the clinical data associated with the patient's pseudonym.

Patient information	
As is commonly done on admission to hospitals, a signed informed consent form will be attached to the administrative and medical file of the patient.
 
In the absence of the signed informed consent form, patients who have undergone CPET will be contacted and informed of the modalities of this study, and asked to sign the informed consent form (see Appendix 1).
 
This will be done as long as it does not involve a disproportionate effort.

Overview and duration of the study	
The data collection will be carried out from February 1, 2023 to December 31, 2023 or during 10 months.
 
The data concerned cover the period from January 2, 2020 to December 31, 2022 (35 months). These data were stored by the investigators on-site as part of their usual practice.
 
The migration of locally stored data to the CPET-STUDIES.COM platform will take place between February, 2023 and December 31, 2023.

Data analysis method	
Analyses will be performed using R software, with all required software packages, and JAGS, in their most up-to-date version at the time of analyses.
 
No hypotheses will be tested for either the primary or secondary objectives. A descriptive analysis of all evaluation criteria will be performed on the total population and on subgroups to be defined a priori according to the sample.
 
The variables collected at the end of the steady state, at maximal exercise, and during recovery (2 min) will be expressed as mean, standard deviation (SD), median, quartiles.
 
Modeling of the kinetics of certain variables (VE TV-BF-HR- RER) will be performed and then a mathematical model will be developed to quantify and compare these kinetics between subgroups. Comparisons of kinetics between subgroups will be made using recently developed mixed-effects functional analysis of variance (FANOVA) methods.

	
The kinetics of some variables will be expressed as a function of developed power (in watts), metabolic power (<math>VO_2</math> in L/min), ventilatory flow (in L/min), HR expressed in absolute value, in % of the max HR reached and in % of the predicted value according to the formula <math>maxHR = 210 - 0.65 \times age</math>).
 
At the request of the scientific committee, additional analyses may be carried out, in particular with regard to the measurement of operating volumes during exercise.

Number of patients	1 000 patients with exercise intolerance following COVID are expected.
Financial partners	Financial support from the Pharmaceutical Group Menarini France and AstraZeneca

*Table of contents*

Synopsis .....	2
1. Introduction .....	9
2. Objectives of the study .....	9
2.1. Primary objective.....	9
2.2. Secondary objectives .....	9
3. Investigators and organization of the study .....	9
3.1. Study data manager.....	9
3.2. Coordinating investigator and principal investigators of the study .....	9

TV	Tidal Volume

## 1. Introduction

Since the first wave of COVID, pulmonologists, cardiologists and physiologists are regularly consulted for intolerance to exercise expressed by dyspnea and/or frank fatigability sometimes associated with muscular or thoracic pain. When these complaints persist beyond 3 months after the first symptoms, it is legitimate to perform a CPET:

- Either to evaluate the functional impact of an identified organ deficiency (e.g. myocarditis, pulmonary fibrosis, etc.),
- Or, in the absence of formal arguments for an identified organ deficiency, to observe possible abnormalities in physiological responses during an incremental exercise test, likely to explain the persistence of symptoms and intolerance to exercise

The recent literature highlights the presence of non-specific ventilatory and cardio-circulatory abnormalities leading to various physio-pathological observations. These preliminary reports concern today small numbers of patients mixing subjects whose clinical forms of COVID, comorbidities and habitus are very diverse. Moreover, the hypotheses or conclusions proposed by these studies are influenced by the medical specialty of the practitioner who observes them.

Thus, it seems necessary to collect a very large number of clinical and physiological observations in order to draw up a factual report of the disorders observed without any interpretative preconception.

## 2. Objectives of the study

### 2.1. Primary objective

**Kinetics of physiological responses and symptoms during CPET:** to describe by homogeneous subgroups of patients, the physiological responses and symptoms during CPET in COVID-19 subjects with persistent symptoms responsible for exercise intolerance.

Homogeneous patient subgroups will consider:

- the initial clinical presentation of COVID,
- any persistent symptoms other than exercise intolerance,
- clinical characteristics prior to COVID-19 infection (co-morbidities – regular habitual physical activity).

### 2.2. Secondary objectives

- To model the kinetics of ventilatory pattern responses in order to characterize the behavior of excessive hyperventilation and, possibly, chaotic breathing.
- To test, through different statistical models, the possibility of predicting the persistence of dyspnoea as a function of exercise variables, pre-existing clinical data of the COVID, clinical presentation of the acute COVID.

### 3.3. Steering committee of the study

The steering committee is composed of 9 members.

#### *3.4. Centers and investigators*

The investigators are Pulmonologists, Cardiologists and Physiologists involved in the realization and the diagnostic interpretation of the Cardio Pulmonary Exercise Testing - CPET within public or private structures (Univ. Hospitals, General Hospitals, private practices or mixed).

About 40 investigators are expected.

#### *3.5. Management center and statistical analysis*

The data management of the study will be carried out by the aCCPP.

A telephone number and an e-mail address will be made available to the participating physicians. The management center will respond to each specific request throughout the study.

Data management is provided by the aCCPP and its contractors.

Statistical analysis will be performed by [name], IMAG Univ. Grenoble Alpes, and [name] [name], MultiDisciplinary Institute in Artificial Intelligence (MIAI) Grenoble Alpes University.

#### *4.1. Constitution of the cohort and data collection*

- ⇒ From June 1, 2022, pulmonologists, cardiologists and physiologists performing functional exercise tests (CPET), in public or private structures (univ. hospital, general hospital, private practice or mixed) will be officially invited to participate in this study by e-mail.
- ⇒ Between June 1, 2022 and November 31, 2023, each physician willing to participate in the study will transmit his signed investigator participation form to the management center, and will receive in return the study documents as well as the instructions to implement in their ergospirometer a standardized export file.
- ⇒ This study will take place over a period of 18 months from June 1, 2022 to December 31, 2023. The data collection concerns patients who had a consultation between January 2, 2020 to December 31, 2022. Therefore, the investigating physicians will identify the files of patients who meet the inclusion criteria of the protocol (§ 5.3), going back to January 2, 2020.

⇒ Once these steps are validated, the investigator will be able to migrate the data (Physiological CPET and Clinical) to the CPET-STUDIES.COM platform, where it will be pseudonymized before any processing.

#### **4.2. Data migration**

Data migration will be performed on the dedicated CPET-STUDIES.COM platform between February 1, 2023 and December 31, 2023.

### **5. Population of the study**

#### **5.1. Recruitment procedures**

All patients with exercise intolerance during COVID, diagnosed between January 2, 2020 and December 31, 2022, who have been informed that the physiological data collected during the CPET and the clinical data necessary for its interpretation may be used for clinical research, can be enrolled.

#### **5.2. Number of Patients**

This study is expected to collect data from approximately 1 000 patients.

#### **5.3. Eligibility Criteria**

Patients with the following characteristics can be enrolled in this study:

- Age ≥ 18 years
- Patients with persistent symptoms 3 months after the onset of COVID-19 infection, regardless the severity of the initial illness
- Patients with an ICU stay, primarily following rehabilitation management; that is, in practice, at least 6 months after COVID
- Patients followed by a pulmonologist, cardiologist or physiologist in a public or private facility or in private practice, allowing for CPET
- Patients who have performed a CPET before January 1, 2023
- Patients informed of the possible anonymized processing of the data collected during CPET for research purposes; and who gave informed consent

#### **5.4. Exclusion Criteria**

Patients with the following characteristics will not be enrolled in this study:

- Age < 18 years
- Patients unable to perform CPET for locomotor reasons
- Patients with severely reduced functional work capacity
- Patient deprived of liberty by judicial or administrative decision
- Patients unable to give informed consent

#### **5.5. Previous and/or concomitant treatments**

As the study is non-interventional, no treatment is prohibited.

### **6. Evaluation criteria**

#### **6.1. Primary endpoint**

To describe by homogeneous patient subgroups, physiological responses and symptoms during CPET in COVID subjects with persistent symptoms responsible for exercise intolerance.

Homogeneous patient subgroups will consider:

- the initial clinical presentation of COVID,
- any persistent symptoms other than exercise intolerance,
- clinical characteristics prior to COVID-19 (co-morbidities - physical activity level).

#### **6.2. Secondary endpoints**

- To model the kinetics of ventilatory pattern responses in order to characterize the behavior of excessive hyperventilation and, possibly, chaotic breathing.
- To test, through different statistical models, the possibility of predicting the persistence of dyspnoea as a function of exercise variables, pre-existing clinical data of the COVID, clinical presentation of the acute COVID.

### **7. Procedures of the study**

## 7.1. Recruitment of pulmonologists, cardiologists, physiologists and patients

The recruitment of investigating physicians for this study is based on a voluntary basis.

The list of potential investigating centers corresponds to certain pulmonology, cardiology and physiology departments involved in the realization and diagnostic interpretation of CPET; whether within public or private structures (univ. hospital, general hospital, liberal or mixed activity).

Pulmonologists, cardiologists and physiologists will be invited to participate in the study by an e-mail from the investigating coordinator. An investigator participation form to be completed by the physicians agreeing to participate in the study will be attached to this e-mail. Physicians agreeing to participate in the study will return the completed form to the study management center before November 31, 2003.

All patients meeting the enrollment criteria and having had exercise intolerance during COVID, diagnosed between January 2, 2020 and December 31, 2022, will have been informed that the physiological data collected during the CPET and the clinical data necessary for its interpretation will be possibly exploited for an observational research (see above 5.1. Recruitment procedures).

## 7.2. Data collection

### 7.2.1. Clinical data

Clinical data recorded (see [Appendix 2](#)) include:

#### **Patient**

- Sex, month and year of birth, weight, height,
- Pre-COVID physical activity level (PA): sport (h/week), PA at work, daily PA, time spent sitting,
- Main comorbidities (pulmonary, hypertension, cardiovascular, metabolic, chronic renal pathologies, psychiatric pathologies, cancers),
- Common treatments (therapeutic class) with potential effects on exercise tolerance.

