## Appendix 2: CPET post-COVID questionnaire

Anonymized Center Code	Anonymized patient code	Sex	Age	Weight	Height
////	////	M/F	years	kg	cm

Date COVID	Date CPET (EFX)
month/year	day/month/year

Physical Activity Level before COVID-19							
Sport (h/week)		Work Activities		Daily Physical Activities			Seating Time
No	No						
YES	YES						< 4 h
< 4 h	With movement	Mainly Domestic (Inside)					4 – 7 h
4-6 h	Without movement	Leisure Time Activities (Outside ≥ 60 min /J)					> 7 h
6 à 10 h							
> 10 h							
Sport competition							

Main comorbidities							
Pulmonary Disease	Arterial hypertension	Cardiac Disease	Metabolic Disease	Chronic renal failure	Chronic Hepatic failure	Psychiatric condition	Cancer
No	No	No	No	No	No	No	No
YES	YES	YES	YES	YES	YES	YES	YES
Obstructive		Myocardiopathy	DT2			Anxiety Treated	Cured
Interstitial		Coronary disease	DID			Dépression Treated	Remission
Vascular		Valvular disease	Thyroid Insufficiency			Psychosis	Progression
Others		Congénital Disease	Others			Cognitive disorder	
		Chronic Heart Failure					
		Others					

COVID: initial clinical presentation							
Besoin en O2		CT-scan Parenchyma Extension			Symptomes non respiratoires		
No		No			No		
YES		YES			YES		
0.5-6 L/min		Mild < 10 %			Prolonged fever		
> 6 L/min		Moderate 10-24 %			Fatigue		
Hight Flow		Moderate-to-severe 25-49 %			Joints/muscle pain/stiffness		
Invasive ventilation		Severe ≥ 50 %			Headache		
					Anosmia and/or agueusia		
					Gastrointestinal		
					Neurological		
					Cardiac/Pericardial		

Symptoms Post COVID													
Dyspnoea	Fatigue	Cough	Muscle/ Joint pain	Anxiety	Agueusie	Anosmia	Headhache	Neurological	Gastro intestinal	Palpitations	Vertigo	Others	
No	No	No	No	No	No	No	No	No	No	No	No	No	No
Yes	Yes	Yes	Yes	Yes	Yes	Yes	Yes	Yes	Yes	Yes	Yes	Yes	Yes
Gasping for breath													
Shortness of breath													
Chest tightness													
Incomplete or unsatisfactory breathing													

Cardiac Evaluation																	
ECG				Echocardiography						MRI							
No		No						No									
Yes		Yes						Yes									
Normal		Normal						Normal									
Abnormal		Abnormal						Abnormal									

Questionnaires Scores													
Hosp. Anxiety and Depression Scale							Chalmers						
Anxiety		Depression						Fatigue					
Not Done		Not Done						Not Done					
Value		Value						Value					

Rest Pulmonary Function													
FEV 1		FVC		SVC		TICO							
(L.)		(L.)		(L.)		(mlco/min/mmHg)							
Value		Value		Value		Value							

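### Comorbidity is a pre-COVID subgroup axis and predictor, but the form records comorbidities without onset, so disease that began after COVID may be counted as pre-COVID

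*Protocol*

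**What the plan says.** The Protocol (Synopsis, 2.1 and 6.1) names three things that the homogeneous subgroups will consider: "the initial clinical presentation of COVID", "any persistent symptoms other than exercise intolerance", and "clinical characteristics prior to COVID-19 infection". The third is spelled out in 6.1 as "clinical characteristics prior to COVID-19 (co-morbidities - physical activity level". The time reference therefore applies to comorbidities and to physical activity alike.

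Sections 2.2 and 6.2 add a prediction objective for persistent dyspnoea. One of its predictor groups is clinical data that existed before COVID.

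Under Patient, section 7.2.1 lists "Pre-COVID physical activity level (PA" and, separately, "Main comorbidities (pulmonary, hypertension, cardiovascular, metabolic, chronic renal pathologies, psychiatric pathologies, cancers". In Appendix 2 the activity block is headed "Physical Activity Level before COVID-19", while the heading of the comorbidity block carries no time reference. Its tick options include interstitial and vascular lung disease, myocardiopathy, treated anxiety and treated depression. The form takes the month and year of COVID and the date of the CPET, but no date for any comorbidity.

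**The concern.** One axis has two halves and they are collected differently. Activity is tied to the time before infection in the text and on the form; comorbidity is tied to no time at all.

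The gap matters here because every patient is seen well after the infection that divides prior from later disease. Eligibility (5.3) requires symptoms still present 3 months after onset. Clinical data come from the medical file (Synopsis, Data collection), and 4.2 places migration in 2023 for COVID going back to January 2020. By then the file may hold diagnoses made after infection. The protocol expects such patients: its first reason for a CPET is "Either to evaluate the functional impact of an identified organ deficiency (e.g. myocarditis, pulmonary fibrosis, etc".

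Two uses of the data are exposed. In the primary description, a subgroup labelled as pre-COVID comorbidity could contain consequences of COVID. In the prediction models, a consequence of COVID could enter as a pre-existing predictor of dyspnoea, which could distort what the models say about prediction from pre-COVID data.

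**Working it through.** There is no figure in the plan to reproduce. The expected 1 000 patients (section 9) come without a calculation, and section 8 states that no hypotheses are tested. The check is one of text, followed by an illustration.

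**Text check.**

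| Item on the third axis | Time reference in the objective (2.1, 6.1) | In 7.2.1 | In Appendix 2 |
|---|---|---|---|
| Physical activity | before COVID | before COVID | before COVID |
| Comorbidities | before COVID | none | none |

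The other fields do not supply the missing onset. Initial severity, CT extension and cardiac or pericardial involvement describe the acute illness. The post-COVID block records symptoms. ECG, echocardiography and MRI are recorded as normal or abnormal, and resting lung function as values; neither gives onset or cause. Anxiety can appear twice, as a post-COVID symptom and, if treated, as a comorbidity, with nothing to show which came first.

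**Illustration (none of these rates is in the documents).** Let
- p = share of patients with true pre-COVID disease of the listed kinds;
- q = share of the others with such disease diagnosed since COVID;
- f = share of those later cases that are ticked in the comorbidity block.

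Misfiled share of the comorbidity subgroup = q·f·(1 − p) / [p + q·f·(1 − p)]. With N = 1 000:

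| p | q | f | Misfiled | Ticked in all | Share |
|---|---|---|---|---|---|
| 30% | 5% | 0.5 | 17.5 | 317.5 | 5.5% |
| 20% | 10% | 0.5 | 40 | 240 | 17% |
| 20% | 10% | 1 | 80 | 280 | 29% |
| 10% | 20% | 1 | 180 | 280 | 64% |
| any | any | 0 | 0 | 1 000·p | 0% |

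The first and fourth rows are the extremes for p from 10% to 30%, q from 5% to 20% and f from 0.5 to 1. The result depends heavily on f, which is how physicians read an unlabelled block. About 40 investigators from three specialties are expected (3.4), and f may differ between them. At p = 20% and q = 10%, a centre that enters only prior disease has 0% misfiled and a centre that enters all current disease has 29%. The database would not show which is which.

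**The case against.** The strongest reply is that a comorbidity ordinarily means a pre-existing condition. Section 7.2.1 places the list under Patient, apart from the COVID pathology list, and the objective itself says prior to COVID. A physician who has read it would enter prior disease only, and f would be zero. No passage tells investigators to enter later disease as a comorbidity. This stands, and for that reason the point is one of possible misfiling. A reader might infer that post-COVID disease is in fact being filed as pre-COVID; the documents do not show that.

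A reader might also infer that the subgroups wrongly mix the two reasons for CPET given in the Introduction, and that an axis for identified organ deficiency is missing. The documents do not support calling that an error. The Introduction gives reasons for ordering a test, not strata. The three axes are things the subgroups will consider, not a closed list, and section 8 leaves subgroup studies to a committee. Acute severity, CT extension, cardiac tests and lung function already allow a partial split. Such an axis is optional.

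Thirdly, the gap is not beyond repair. The referring physician can still identify the patient (Synopsis) and could return to the file where it dates the disease. That is true, but it means going back to the sites. Neither a statistical analysis plan nor the committee can derive from the database an onset that was never entered.

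**Conclusion.** The point holds in a limited form. The objective and endpoint require comorbidity before COVID, and a secondary objective requires pre-existing data, but the collected field cannot establish either. Post-COVID disease may therefore be counted as pre-COVID comorbidity.

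The extent cannot be determined from the documents. It is zero if all physicians enter prior disease only. The range of 5.5% to 64% rests wholly on assumed values of p, q and f and shows only that the effect need not be small; it is not an estimate. What is certain is the mismatch between the axis and the form, and that the data as recorded would not reveal how large the effect was. The sample size is not affected.

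**What to change.** In 7.2.1 and Appendix 2, mark each positive comorbidity as before COVID, since COVID or unknown. The date of COVID is already on the form, so the physician needs only to place the diagnosis relative to it. In 2.1, 2.2, 6.1 and 6.2, state that only entries marked before COVID feed the pre-COVID axis and the pre-existing predictors, and report the share marked unknown. For records already migrated, ask the referring physician to add the mark from the file.

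The cost is one extra tick per positive comorbidity, read from the same medical file, plus queries for any records already entered. Some onsets will not be datable, and the unknown category makes that visible.
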